### **Mean change from baseline in AUC glucose obtained during MTT at Week 24, only applicable for subjects in China**

For the mean change from baseline in area under the curve (AUC) of glucose obtained during an MTT, the change in AUC will be estimated based on the Trapezoidal rule using the estimates of change from baseline at Week 24 in postprandial measurements at target times t1, t2, t3, t4 and t5 (0, 30, 60, 120, and 180 minutes respectively after administration of a meal).

To incorporate the correlations among post-prandial measurements at different MTT target time points and an appropriate representation of effect of baseline measurements, the change from baseline at Week 24 in postprandial measurements will be analysed using a longitudinal repeated measures method. The model will include the fixed categorical effects of treatment,

stratum, target time and treatment-by-target time interaction as well as the continuous fixed covariate of baseline measurement at target time 0 of MTT, with an assumption of unstructured matrix for within-subject error variance-covariance if applicable. The SAS® procedure PROC MIXED will be used.

After obtaining the estimates of mean change from baseline at Week 24 in postprandial measurements, the mean change in AUC within a treatment group or difference in mean change in AUC between treatment groups will be estimated within the framework of the mixed model, using the formula based on the Trapezoidal rule:

$$\overline{\Delta AUC} = \sum_{i=1}^4 (t_{i+1} - t_i) \frac{\hat{y}_{t_{i+1}} + \hat{y}_{t_i}}{2}$$

where  $\hat{y}_{t_i}$  is the estimate of mean change from baseline at target time  $t_i$  in a treatment group for estimation of mean change in AUC within treatment group, and for estimation of difference in change in AUC between treatment groups,  $\hat{y}_{t_i}$  is the estimate of mean difference between treatment groups in change from baseline at target time  $t_i$ . The variability of  $\overline{\Delta AUC}$  will also be estimated within the framework of the mixed model in SAS.

Point estimates and 2-sided 95% confidence intervals for the mean change within each treatment group, as well as the difference in mean change between each dapagliflozin treatment group and placebo at each target timepoint, will be calculated.

### **Mean percent change from baseline in fasting serum lipids (Total-C, LDL-C, HDL-C, TG)**

The mean percent change from baseline to Week 24 in fasting serum lipids will be analysed separately, using ANCOVA models, as outlined in Section [4.2.4.2](#).

The natural logarithms of the post- to pre-treatment ratios, and the natural logarithm (Ln) of the baseline lipid measurement, will be used in the model. Subsequently, the estimates from the analysis will be back-transformed to original values for reporting in the tables.

Point estimates and 2-sided 95% confidence intervals for the mean change within each treatment group, as well as the difference in mean change between each dapagliflozin treatment group and placebo, will be calculated.

### **HbA1c and FPG Analyses in Open-Label**

HbA1c and FPG will be summarised descriptively over time for the open-label treatment period. In addition, the proportion of subjects with HbA1c at Week -2, categorized as [ $<7\%$ ,  $\geq 7\%$  and  $\leq 10.5\%$ ,  $>10.5\%$ ], will be summarised using the Open-label Treated Subjects Analysis Set.

## 4.2.5 Safety analyses

Safety analysis, including adverse Events (AEs) and laboratory marked abnormalities (MA), for open-label treatment period will be conducted using open-label treated subjects analysis set.

Safety analyses of the double-blind treatment period will be performed using safety analysis data set, including data after rescue (primary safety analysis). Additional sensitivity analyses for AEs and laboratory MA will be performed excluding data after rescue for the double-blind treatment period. The primary analyses of events of hypoglycaemia will be performed excluding data after rescue.

### 4.2.5.1 Adverse Events

AEs will be classified by Primary SOC and PT according to the MedDRA. Summaries of AEs will use the version of MedDRA that is current at the time of database lock.

In summaries by SOC and PT, AEs will be sorted by overall decreasing frequency within each SOC and PT. In summaries by PT, AEs will be sorted by decreasing frequency within PT according to the highest of either of the combinational dose group across the study.

Separate pages to capture events of hypoglycaemia are contained within the CRF. Hypoglycaemia or discontinuation due to hypoglycaemia would not be reported on an AE CRF page unless the event fulfilled criteria for an SAE in which case a serious AE (SAE) form would be completed. Hypoglycaemia events that are reported as SAEs will be included in all summaries of AEs or SAEs. Separate summaries will be provided including hypoglycaemia events reported on the special CRF pages.

Analysis of AE will be on treatment-emergent AEs for open-label treatment period and double-blind treatment period, as defined in section [3.5.1](#).

### All Adverse Events

An overall summary of adverse events at subject level, including TEAEs, TESAEs, death, hypoglycaemia, severe events, treatment-related events, events leading to the discontinuation of study medication, events leading to death will be presented for open-label treatment period, double-blind treatment period and double-blind treatment period prior to rescue, respectively.

All TEAEs (serious and non-serious, excluding hypoglycaemic events that are not reported as SAEs) will be summarised by SOC and PT for double-blind treatment period. In addition, a subject listing of all reported AEs will be produced, displaying all events including pre-treatment AEs and post-treatment AEs, if any. All TEAEs (serious and non-serious) including all hypoglycaemic events will also be summarised by treatment group, where applicable.

In addition, the following summaries will be provided for the double-blind treatment period (excluding hypoglycaemic events that are not reported as SAEs):

- Most common TEAE by PT and treatment group (i.e., reported by  $\geq 2\%$  of subjects in any treatment group),
- TEAEs by SOC, PT, intensity and treatment group,
- TEAEs related to study medication (by investigator) by SOC, PT and treatment group.
- Proportion of subjects with TEAEs by SOC and PT in subgroups of subjects defined by age category ( $< 65$  and  $\geq 65$  years), gender and race.

No formal comparisons will be made between treatments. No formal statistical testing will be performed, only summary statistics will be provided.

### **Serious Adverse Events**

TESAEs (including hypoglycaemic events) occurring during the double-blind treatment period will be summarised by SOC, PT and treatment group. In addition, the proportion of subjects with related TESAEs will be presented by SOC, PT and treatment group. TESAEs (including hypoglycaemic events) occurring during the open-label treatment period will be summarised by SOC and PT for Open-label treated subjects analysis set.

A listing of all SAEs will be produced, displaying all SAEs (including pre-treatment SAEs and post-treatment SAEs) that occurred during the study.

### **Adverse Events Leading to Discontinuation of Study Medication**

AEs with an onset during the double-blind treatment period reported with an action taken of discontinuation of study medication will be summarised by SOC, PT and treatment group. This summary will include hypoglycaemia events that reported as SAEs. When summarising AEs leading to discontinuation no upper cutoff day windows are applied.

In addition, a subject listing of discontinuation due to AEs will be provided, displaying all events that led to discontinuation that occurred during the study.

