### **3.9 Discontinuation of investigational product**

#### **3.9.1 Procedures for discontinuation of a subject from investigational product**

Subjects MUST discontinue IP for any of the following reasons:

- Subject decision. The subject is at any time free to discontinue treatment, without prejudice to further treatment
- Subject experiences an AE or SAE that, in the investigator's opinion, necessitates discontinuation from study medication
- Pregnancy confirmed by a positive pregnancy test or otherwise verified
- Serious hypersensitivity reaction
- Acute pancreatitis

- Severe non-compliance with the study protocol
- Loss of ability to freely provide consent through imprisonment or involuntary incarceration for treatment of either a psychiatric or physical (e.g., infectious disease) illness
- eGFR < 60mL/min/1.73m^2 for sustained period of time (16 weeks)

**Note: Dapagliflozin based on its MOA has been shown to reduce eGFR by up to 10% with initiation of therapy; however, this has in general been reversible and not resulted in renal failure and eGFR values returned to baseline within 12 - 24 weeks of continued therapy.**

- Initial and repeat laboratory tests meet any of the following criteria:
  - ALT and/or AST are >3 x ULN and TB >2 x ULN
  - ALT and/or AST are >5 x ULN for ≥14 consecutive days, at any time after initial confirmatory results
  - ALT and/or AST are >8 x ULN
- Consider to temporary interrupt dapagliflozin if DKA is suspected. The subject should be promptly evaluated. If DKA is confirmed, dapagliflozin should be discontinued permanently.
- Hypoglycaemia events as defined in Section 3.9.2.

Note: Discontinuation of non-IP at the discretion of the investigator should be reported to Sponsor and recorded in eCRF.

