### **Hypoglycaemia Events**

Hypoglycaemia may be an expected event in subjects who are treated for diabetes. Subjects and their family members must be aware of the possibility that hypoglycaemia may occur and the dangers associated with low blood sugar.

Study subjects must be properly instructed on the recognition and management of hypoglycaemia. Subjects should record in their diaries any hypoglycaemic symptoms. They should be encouraged to measure, when possible, their blood glucose values when they have symptoms of hypoglycaemia. Subjects should carry with them easily ingestible forms of carbohydrate at all times in order to treat an event of hypoglycaemia should it occur.

During clinical trials, subjects frequently report symptoms of hypoglycaemia when asked, even when treated with placebo or medications not otherwise associated with hypoglycaemia. As hypoglycaemia is an important event associated with diabetes therapy, all episodes which could be consistent with the clinical definition of hypoglycaemia **as assessed by the investigator** should be documented and reported on the appropriate eCRF page.

Hypoglycaemia eCRF pages will be used to document all reported episodes of hypoglycaemia. **The investigator is responsible for questioning the subject about all symptoms reported on the hypoglycaemia log and for determining if they meet the clinical definition of hypoglycaemia. Only symptoms and/or blood glucose values deemed by the investigator to meet the definition of hypoglycaemia should be reported on the hypoglycaemia eCRF pages.** Signs and symptoms of hypoglycaemia, hypoglycaemia episode or discontinuation due to hypoglycaemia should not be reported on the AE eCRF page, unless the event fulfils protocol criteria for a SAE (see Section 6.2), in which case an SAE form must be completed in addition to the hypoglycaemia eCRF pages for hypoglycaemia.

The diary will be returned by the subject and reviewed by site personnel at every subsequent visit. Completed diary pages will be added to the subject's source record, and data from the diary will be entered in the appropriate eCRF. A new diary for the next period will be handed over to the subject if needed.

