### **4.4 Early termination analyses**

On Jun 30, 2020 AstraZeneca decided to stop commercialization of QTERNMet/Qtrilmel and to withdraw all active licenses, for business reasons. DS-NAVIGATION will be closed without recruiting subjects in China and patients recruited from Thailand and Vietnam will complete the study.

Therefore, the planned analyses in this study will be conducted over all data available. To support the synopsis format CSR, the following analysis will be performed:

- Summaries of subject disposition, summaries in the Enrolled subjects set and Open-label treated subjects analysis set, as described in Section 4.2.1. Subject disposition will also be listed.
- Summary of analysis set, defined in Section 2.1.
- Demographic and baseline characteristics as described in Section 4.2.2 and Section 4.2.2.1.
- An overall summary of adverse events at subject level, including TEAEs, TESAEs, death, hypoglycaemia, severe events, treatment-related events, events leading to the discontinuation of study medication, events leading to death will be presented for open-label treatment period and double-blind treatment period. TEAEs will also be summarised by SOC and PT in open-label and double-blind treatment. TESAEs will be summarised by SOC and PT in the double-blind period only. AEs and SAEs will also be listed.
- Important protocol deviations, observed HbA1c data, and marked abnormalities by test will be listed.

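### The summary of adverse events leading to discontinuation omits subjects who stop investigational product only for non-serious hypoglycaemia, and no other specified output counts them by arm

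*SAP*

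**What the plan says.** **Stopping IP.** Protocol section 3.9.1 opens its list with "Subjects MUST discontinue IP for any of the following reasons" and includes "Hypoglycaemia events as defined in Section 3.9.2". Section 3.9.2 names repeated symptomatic episodes, or more than one severe episode, as possible indications, subject to the investigator's opinion. It does not require the event to be serious.

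**Recording.** Protocol section 5.2.5.1 sends hypoglycaemia to its own eCRF pages and adds that "discontinuation due to hypoglycaemia should not be reported on the AE eCRF page, unless the event fulfils protocol criteria for a SAE". Footnotes f and 6 to protocol Table 1 repeat the rule. SAP section 4.2.5.1 has the same rule: "Hypoglycaemia or discontinuation due to hypoglycaemia would not be reported on an AE CRF page unless the event fulfilled criteria for an SAE".

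**Reporting.** Under *Adverse Events Leading to Discontinuation of Study Medication*, SAP section 4.2.5.1 takes double-blind AEs "reported with an action taken of discontinuation of study medication will be summarised by SOC, PT and treatment group". It then adds: "This summary will include hypoglycaemia events that reported as SAEs".

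**After early termination.** SAP section 6 says that only the analyses in section 4.4 will be run. Section 4.4 keeps an overall AE summary in which "events leading to the discontinuation of study medication" is one item and hypoglycaemia is another.

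**The concern.** The share of subjects who stop treatment because of adverse events is one of the first tolerability figures a reader looks for. Hypoglycaemia is the first AE of special interest named in both documents, and the protocol makes it a stopping reason. A reader of the discontinuation table would expect it to include subjects whose treatment ended because of hypoglycaemia. Under the recording rule it includes them only if the event was also an SAE.

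The SAP deals with the same problem elsewhere. Treatment-emergent AEs are summarised without non-serious hypoglycaemia and then again with all hypoglycaemic events included. The discontinuation summary has no second version.

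**Working it through.** No arithmetic applies. The documents give no expected rate of stopping for hypoglycaemia and no figure to reproduce. The check follows one case through the rules and then looks for another output that would catch it.

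**Following the case**

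1. A subject has repeated symptomatic episodes, none meeting the SAE criteria in protocol section 6.2, and the investigator stops IP. Protocol sections 3.9.1 and 3.9.2 allow this.
2. Under protocol section 5.2.5.1, neither the episodes nor the discontinuation goes on the AE page.
3. So there is no AE record with discontinuation of study medication as the action taken.
4. The discontinuation summary in SAP section 4.2.5.1 draws on such records, so the subject is not counted.
5. If one episode had met an SAE criterion, an SAE form would also have been completed and the subject would be counted.

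The summary's own sentence does not contain the word *only*. The restriction comes from steps 2 and 3. The subject would also be counted if a different AE with the same action taken had been recorded.

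Severity does not guarantee inclusion. Protocol section 6.3.7 defines severe hypoglycaemia by third-party assistance, recovery, neuroglycopenic symptoms and glucose level if available. Section 6.2 sets separate criteria for an SAE.

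**Looking for another output**

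| Output | SAP section | What it gives | Hypoglycaemia-driven stops by arm? | Named in 4.4? |
|---|---|---|---|---|
| AEs leading to discontinuation, by SOC and PT | 4.2.5.1 | AE records with action taken | Serious events only | No |
| Listing of discontinuations due to AEs | 4.2.5.1 | Individual events | No, a listing | No |
| All treatment-emergent AEs including all hypoglycaemia | 4.2.5.1 | Occurrence | No | Not in that form |
| Hypoglycaemia summaries and listing | 4.2.5.1, Table 4 | Subjects, events, ADA class | No | No, apart from the hypoglycaemia item in the overall summary |
| Withdrawal from treatment by reason | 4.2.1 | Reasons by arm | No hypoglycaemia category specified | Yes |
| Overall AE summary | 4.2.5.1, 4.4 | Hypoglycaemia and discontinuation as separate items | Source of the discontinuation row not stated | Yes |

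No output is specified to give the count. The last is the only one still to be produced in which the gap matters.

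**The case against.** The other side has several good points.

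- **The rule is open and consistent.** Protocol and SAP state it in the same sense and provide separate hypoglycaemia reporting. This stands: it is a reporting gap, not a contradiction, and it touches no efficacy hypothesis.
- **The subject is not lost.** A reader might infer that these stops vanish from the report. They do not. The subject is in the disposition summary, and recorded episodes are in the hypoglycaemia outputs. What is missing is the link between the two. One qualification: protocol section 6.3.7 keeps symptomatic episodes without a glucose reading out of the eCRF altogether, so a stop based on those alone might leave no hypoglycaemia record either.
- **Most of the affected output has been dropped.** SAP sections 4.4 and 6 remove the SOC/PT discontinuation table and its listing. This stands and narrows the point to one row. SAP section 4.2.5.1 attaches its exclusion of non-serious hypoglycaemia to other tables, not to the overall summary, so exclusion from that row is an inference. The dropped listing also carried no stated SAE restriction.
- **Section 3.9.2 is worded as a guideline.** It relies on investigator judgement and advises against stopping for single episodes, while section 3.9.1 places it on a mandatory list. The two passages should be reconciled. On either reading, a non-serious stop is possible.
- **The fix depends on data not shown.** The documents show neither a hypoglycaemia category among the withdrawal reasons nor an action-taken field on the hypoglycaemia page. This stands as a condition on the fix.

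**Conclusion.** The point holds in a limited form. As planned, the AE discontinuation summary does not count a subject who stops IP only for non-serious hypoglycaemia, and no specified output supplies that count by arm. After early termination, what remains is the discontinuation row of the overall AE summary in SAP section 4.4, where the documents do not say whether such subjects are included.

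The size cannot be given. There is no expected rate, and protocol sections 1.1 and 1.3 describe a low risk of hypoglycaemia with these drugs. The planned 114 subjects per arm, about 23 of them from outside China, are not the numbers randomised at closure. Dividing one missed subject by either would not measure the impact.

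A reader might also infer that the omission flatters the dapagliflozin arms. The documents do not support a direction. Rescue with insulin or other agents is allowed in every arm. If placebo subjects were rescued more often, stops for rescue-related hypoglycaemia could fall in the placebo arm.

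The conclusion assumes that sites follow the recording rule and that no other AE was recorded as the reason for stopping.

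**What to change.** In SAP section 4.2.5.1, and for the row kept in section 4.4:

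- Add a per-arm count of subjects whose IP was stopped because of hypoglycaemia, serious or not. Take it from the treatment-withdrawal reason, or from the hypoglycaemia page if that page records action taken.
- Show it as its own row beside the AE-page count.
- Give a combined total for AE or hypoglycaemia leading to discontinuation, counting each subject once.
- State in section 4.4 which pages the discontinuation row draws on.

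Check the eCRF first. If neither source identifies hypoglycaemia as the reason for stopping, a footnote saying that non-serious hypoglycaemia is not counted is the minimum.

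The cost is a little SAP text and programming, and possibly a slightly less favourable discontinuation rate. No stopping or recording rule changes.

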### **Adverse Events of Special Interest**

Event categories of adverse events special interest (AESI) for this study include: hypoglycaemia, volume depletion, cardiac failure (including confirmed adjudicated hospitalization due to cardiac failure events), hypersensitivity reactions, pancreatitis, severe cutaneous adverse reactions, malignancies (including pancreatic cancer, breast cancer and bladder cancer), genital infections, UTIs, liver injury, renal impairment/renal failure, DKA, AEs leading to amputation and potential risk factor AEs for amputations affecting lower limbs (“preceding events”) and fracture.

To identify each type of adverse event of special interest, a list of PTs will be selected before database lock and unblinding of the database.

For each category, the number and percentage of subjects with the event is summarised by PT and treatment group in the double-blind treatment period.

## Hypoglycaemic Events

Separate pages to capture events of hypoglycaemia are contained within the CRF.

Hypoglycaemic events with an onset from Day 1 of double-blind treatment to and including 4 days after the last dose date of double-blind treatment will be considered as occurring during the double-blind treatment period. The proportion of subjects with hypoglycaemic events will be tabulated by treatment group.

Hypoglycaemia episodes will be categorised according to the American Diabetes Association (ADA) Criteria [\[ADA 2018\]](#) which classifies hypoglycaemia as follows:

**Table 4 - Hypoglycaemia classes**

Severe hypoglycaemia:	
An event requiring assistance of another person to actively administer carbohydrate, glucagon, or other resuscitative actions.
 
A hypoglycaemia event will be considered as severe hypoglycaemia if it meets all of the following criteria:
 
 
• Require third party assistance
 
• Prompt recovery after carbohydrate or glucagon administration
 
• Include symptoms of neuroglycopenia (such as dizziness, confusion, lethargy, headache, visual disturbances, difficulty concentrating, speech difficulty, somnolence/prolonged sleep etc.)
 
• Glycaemia level, if available, of less than or equal to 70 mg/dL (3.9 mmol/L)
 

Clinically significant hypoglycaemia:	Glycaemia level < 54 mg/dL (3.0 mmol/L)
Hypoglycaemia alert value	Glycaemia level $\leq 70$ mg/dL (3.9 mmol/L)

Number and percentage of subjects who had any hypoglycaemic event and total number of events by treatment group will be presented for the safety analysis set.

A summary of proportion of subjects having severe hypoglycaemia, clinically significant hypoglycaemia, and hypoglycaemia alert value as categorised by the ADA criteria above will also be presented for the safety analysis set. All incidences of hypoglycaemic events and their ADA categorisation will be listed.

